
### **3. Statistical Methods**

#### **3.1. Planned Sample Size**

A group sample size of 70 per group (recruiting 80 per group to account for a 12% dropout rate), and an assumed SD of 0.46 for the  $\log_{10}$  PRNT titers (A strain) will give 80% power to detect a relative change in titers from the Group 1 of a 66% increase.

Assumptions used to determine the sample size of the trial are below.

- Testing of the primary objective will be performed by assuming that the  $\log_{10}$  of the titers are normally distributed.
- No adjustment for multiple comparison is considered.
- Testing will be conducted in a descriptive manner and no adjustment for multiple testing will be performed.
- The upper 95% confidence limit of the standard deviation (SD) of the  $\log_{10}$  titers from the Phase I trial RSV-MVA-001 at Visit 6 (2 weeks post second vaccination) was calculated as 0.46 (the SD was very similar in all groups). The SD is assumed to be similar to that observed in the RSV Phase I trial (RSV-MVA-001).

#### **3.2. Analysis Populations**

##### **3.2.1 Full Analysis Set (FAS)**

This is the subset of subjects who will have received at least one vaccination and for whom any post-baseline data are available. The primary analysis of safety and efficacy will be performed on this analysis set.

In the case where a subject might receive the wrong randomized treatment, safety summaries for this subject will be based on actual treatment received. However, for a subject randomized to Group 2 or Group 4, and who received only one vaccination instead of two, safety summaries for this subject will be based on their randomized treatment group.

##### **3.2.2 Per-Protocol Set (PPS)**

This is the subset of subjects in the FAS who have received all vaccinations, completed all visits of the active trial phase (Visit 1 to EAP) and adhered to all protocol conditions. Subjects with major protocol violations will not be included in this dataset. However, subjects with only minor (not relevant) protocol deviations are included into this dataset.

The decision whether a protocol deviation is major or not for the classification of subjects into the various datasets will be made on a case-by-case basis at the data review meeting (DRM) prior to database lock.

Potential major protocol violations are (but are not restricted to):

1. Premature discontinuation of the trial during the active trial phase (the question “did the subject prematurely discontinue the trial?” is answered with “yes” even where no other reason exists to exclude the subject from further participation in accordance with the protocol).
2. Subject did not meet all of the inclusion criteria.
3. Subject met one or more of the exclusion criteria.
4. Withdrawal from the second vaccination.
5. Major vaccine preparation and administration deviation from specification as given in the protocol including cases where the subject fulfils at least one of the criteria specified in the protocol for withdrawal from vaccination.
6. Major deviations of the visit window as determined during the DRM(s).
7. Prohibited Prior or Concomitant Medication use.
8. Missing immunogenicity data at any critical visits (the decision on what is a critical visit will be made at the DRM).
9. Respiratory Viral Panel result positive for RSV A or RSV B.

The main analysis of humoral and mucosal immunogenicity endpoints will be performed on the FAS. The same statistical procedures will also be applied to the PPS. If there is no substantial difference in FAS and PPS then only the FAS will be presented in the main part of the CSR.

### **3.2.3 Immunogenicity Analysis Set (IAS)**

This is the subset of subjects in the FAS which was assigned to the PBMC subgroup. The main analysis of the cellular immunogenicity endpoints will be performed on the IAS. Additional subgroups may need to be defined during the DRM before database lock and would be described in the CSR.

## **3.3. Data Definitions, Data Conventions and Handling of Missing Data**

### **3.3.1 Missing Immunogenicity Data**

Analysis of immunogenicity variables will be done on a valid case basis, i.e. for missing observations no imputation technique such as “Last observation carried forward” will be applied, since this could introduce an optimistic bias into the analysis.

For assay results that are below the detection limit, refer to [Table 1](#): Detection Limits (DL) in the general definition section.

### 3.3.2 Missing Adverse Event and Concomitant Medication Data

In the case of incomplete AE and/or medication start and end dates, the following rules will be used to assign AEs to the correct vaccination period, and medications as prior/concomitant:

For analysis purposes of any Prior and Concomitant Medication or any AE, imputation of partial start and end dates will be performed based on the following rules:

| Missing            | Rule for start date | Rule for end date | Flag for imputation |
|--------------------|---------------------|-------------------|---------------------|
| Day                | First of month      | Last of month     | D                   |
| Month † | 1. January          | 31. December      | M                   |
| Year †  | no imputation       | Last visit date   | Y                   |

† It is assumed that a missing month implies a missing day as well, and that a missing year implies a missing month and day.

#### Partial/Missing Start Date

- If day is missing, then impute the 1st of the month as in the table above, but if the month is the same as the month of the first vaccination date then assign the imputed start date as the first vaccination date.
- If month and day are missing, then impute as above to January 1 unless the year is the same as the first vaccination date then assign imputed start date as the first vaccination date.
- If the date is completely missing, then impute the first vaccination date unless the end date indicates that the AE/medication could have started/been taken prior to this in which case the date is imputed to 1st January of the same year as the start date.

#### Partial/Missing End Date

- If day is missing, then impute the last day of the month as in the table above unless the month is the same as the month of the first vaccination date then impute the end date as the last vaccination date.
- If month and day are missing, then impute as above to December 31 unless the year is the same as the first vaccination date then assign imputed end date as the last vaccination date.
- If the date is completely missing, check if AE/medication is ongoing before imputing a date and when the AE/medication started in relation to vaccination date. If the ongoing flag is missing, then assume that the AE/medication is still ongoing/medication is still being taken. In this case, do not impute the date. If the AE/medication stopped and the start date is prior to the first vaccination date, then impute the first vaccination date. If the AE/medication started on or after first vaccination date, then impute an end date which is one day after the last vaccination date.

These imputation methods will be used for the table summaries. However, all listings will display the original dates as captured in the eCRF.

### **3.3.3 Assignment of AEs to Vaccination Period**

Each AE will be assigned to a vaccination period using date/time of vaccination and date/time of onset of the AE:

- All AEs starting at or after the first vaccination but before vaccination 2 (Visit 3) will be assigned to vaccination period 1.
- All AEs starting on or after the second vaccination but before or at EAP will be assigned to vaccination period 2. If the subject missed the second vaccination for any reason, the AEs will be assigned to the overall vaccination period.
- Any AEs starting after EAP up to the FU2 Visit belong to the FU period.

If onset time is missing and start date of AE coincides with the date of a vaccination, the AE will be assigned to the vaccination period corresponding to the vaccination on this date.

Each AE starting on or after first vaccination not matching the definition of a solicited AE is defined as an unsolicited AE. If a solicited AE begins outside of the 8-day period following the last vaccination it will be considered an unsolicited AE regardless of the preferred term (PT). If start time of the AE is missing and start date coincides with date of the vaccination, it will be regarded as a treatment-emergent AE. If the start date is (partially) missing the AE will be regarded as a treatment-emergent AE following the worst-case principle.

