### **Vaccination Period**

A vaccination period is defined as the period starting at a given vaccination and ending 28 days after this vaccination or until the subject receives another vaccination or discontinues the trial with the following hierarchy:

- If subject receives both vaccinations, the second vaccination represents the end of vaccination period 1.
- The end of vaccination period 2 is 28 days after receiving the second vaccination, unless subject discontinues earlier. In this case, the discontinuation date represents the end of vaccination period 2.
- If subject discontinues before second vaccination, the discontinuation date represents the end of vaccination period 1.

As the intention is that all subjects will receive two vaccinations, two vaccination periods will be recorded per subject. The overall vaccination period starts from the beginning of period 1 and ends at the end of period 2.

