#### Worst-case principle:

To avoid a potential misclassification of an AE to a vaccination period or to the overall vaccination period, if an imputed start date corresponds to the first of the month or to the first of the year, and matches the month and year of the first or second vaccination date, then the AE will be assigned to the vaccination period with matching month and year. If the AE cannot be assigned to a vaccination period because of a (partially) missing start date then it will be only assigned to the overall vaccination period.

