### **3.5.8 Adverse Events**

A summary table by vaccination period and Overall will be presented as an overview of local and general solicited AEs and unsolicited AEs. This summary table will present the number and percentage of subjects who had at least one event in each period as well as the corresponding total number of events for:

- At least one AE documented
- Any TEAE
- Non-serious TEAEs
- SAEs
- Related TEAEs
- TEAEs Graded  $\geq 2$
- TEAEs Graded  $\geq 3$
- Related TEAEs Graded  $\geq 3$

- Related SAEs
- AEs leading to withdrawal from the trial
- AEs leading to withdrawal from second vaccination
- Deaths

The Overall summary is the sum of Period 1 and Period 2 counts.

A similar per subject table will be presented where each subject is counted once per their entire study participation.

For the ATP and FU Phase, all AEs will be listed by subject, including SOC and PT for the FAS. Any AE with onset later than 28 days since the previous vaccination will not be included in summary tables but will be included in the listing and will be flagged accordingly as non-treatment-emergent.

According to the clinical trial protocol no new AEs should be reported during the FU Phase, except SAEs and AEs related to respiratory tract infections, but if any are reported then they will be listed but considered non-treatment-emergent and no statistical testing or summaries will be presented for them.

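### Main SAP 3.3.3 and 3.5.8 conflict for subjects who miss the second vaccination: on the likelier reading, their adverse events enter no column of the per-period overview

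*SAP*

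**What the plan says.** Four places in the main SAP bear on where an adverse event (AE) is counted.

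- **Section 3.3.3, first bullet:** "All AEs starting at or after the first vaccination but before vaccination 2 (Visit 3) will be assigned to vaccination period 1". It makes no exception for subjects who never reach dose 2.
- **Section 3.3.3, second bullet (Period 2), last sentence:** "If the subject missed the second vaccination for any reason, the AEs will be assigned to the overall vaccination period".
- **Section 3.3.3, worst-case principle:** an AE that cannot be placed because its start date is incomplete is handled so: "then it will be only assigned to the overall vaccination period".
- **General Definitions, Vaccination Period:** "If subject discontinues before second vaccination, the discontinuation date represents the end of vaccination period 1". The same definition treats the overall period as an interval: "The overall vaccination period starts from the beginning of period 1 and ends at the end of period 2".

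Section 3.5.8 describes the AE overview by vaccination period (Table 14.3.1.1). One of its rows is "AEs leading to withdrawal from second vaccination". After the row list it states: "The Overall summary is the sum of Period 1 and Period 2 counts". A second overview, Table 14.3.1.1.1, does not use periods: "A similar per subject table will be presented where each subject is counted once per their entire study participation".

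**The concern.** A subject who misses dose 2 has two possible homes for the AEs that follow dose 1, namely Period 1 or the overall period, and the SAP does not say which takes precedence. The choice matters because Overall in the overview is a sum of the two periods. An event held in the overall period and in neither component cannot enter that sum.

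The subjects concerned include those who stopped because of an AE after dose 1. In a dose-ranging trial, these are the events that a reader of a per-vaccination safety table will look for. The protocol frames its safety endpoints for Grade 3 or higher related AEs and for unsolicited AEs as the four weeks after each vaccination, and the per-period tables present that view. Section 3.2.1 says how one-dose subjects of Groups 2 and 4 are to be summarised for safety, so the SAP means to keep them in the tables.

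**Working it through.** There is no planned figure to reproduce. The check applies the stated rules to cases.

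**Scope of the sentence.** Read narrowly, the one-dose sentence covers only the window of its own bullet, from the second vaccination to EAP. These subjects have no second vaccination, and protocol 4.2.4 moves their EAP to four weeks after dose 1. The narrow reading therefore leaves the sentence almost nothing to act on. This makes the broad reading (all AEs of such a subject) the natural one, but does not prove it.

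**Illustration.** Take five invented events:

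- Subject A, two doses: one event on day 3 and one on day 30.
- Subjects B and C, dose 1 only: one event each (days 5 and 10), each leading to withdrawal from dose 2.
- Subject D, two doses: one event supposed to be unplaceable in time.

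| Rule applied | Period 1 | Period 2 | Neither | Overall as sum | Dose-2 withdrawal row |
|---|---|---|---|---|---|
| Broad reading of the one-dose sentence | 1 | 1 | 3 | 1 + 1 = 2 of 5 | 0 of 2 |
| First bullet prevails | 3 | 1 | 1 | 3 + 1 = 4 of 5 | 2 of 2 |

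If Overall also counts events assigned only to the overall period, it is 5 of 5 and the withdrawal row is 2 of 2 in Overall under either reading. The per-subject overview and Listing 16.2.7.1.6 show 2 of 2 throughout.

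**Why the row goes to zero on the broad reading.** Everyone with an AE leading to withdrawal from dose 2 has missed dose 2. All their AEs then sit in the overall period alone, so the row is 0 in Period 1, 0 in Period 2, and 0 + 0 = 0 in Overall.

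**The undated event.** Subject D's event is lost from the sum under both readings. In practice this class is small: section 3.3.2 imputes a start date when the day is missing, when day and month are missing, and when the whole date is missing.

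**Scale.** No document gives a rate of missed second doses. As an assumption only, let it run from 0 to the 12% dropout used for the sample size (main SAP 3.1), which is a different quantity. Then 0 to 0.12 × 400 = 48 subjects would be affected, or 0 to 0.12 × 80 = 9.6 per group. The number of events that this represents cannot be derived.

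**The case against.** The best defence is that the text permits a harmless reading. The one-dose sentence does not say that assignment to the overall period is exclusive, whereas the worst-case rule just after it does. The first bullet covers all AEs before vaccination 2, and the General Definitions give a subject who discontinues a Period 1. Because the overall period begins with Period 1, an AE could belong to both. The narrow reading also has some content: a subject found ineligible at Visit 3, due 28 to 35 days after Visit 1, goes on to EAP, and the sentence could cover AEs around that point.

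This stands as far as it goes. A reader might infer that the withdrawal row is bound to be empty and must lose all its events. The documents do not support that, because the result follows from one reading of an ambiguous rule.

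Two further points stand. The additive rule is written for the overview table. The text on unsolicited AEs in 3.5.8 asks for an overall summary without saying that it is a sum, so an Overall column there could keep the events even on the broad reading; the Period 1 column would not. And the information is not lost to the report: Table 14.1.2 gives reasons for withdrawal from the second vaccination, the per-subject AE tables do not depend on periods, and Listing 16.2.7.1.6 names the events.

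The defence does not remove the conflict. Nothing states precedence, and a programmer who applies 3.3.3 broadly and 3.5.8 literally produces a wrong count.

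**Conclusion.** The rules contradict each other and need correction. On the broad reading of 3.3.3, the AEs of one-dose subjects appear in no column of Table 14.3.1.1, its dose-2 withdrawal row reads zero, and the Period 1 columns of the other per-period AE tables omit the same events. If the first bullet prevails, only events assigned solely to the overall period are lost, and few are likely. In the first case the report would contradict itself, with a zero in one overview and events in the per-subject overview, the disposition table and the listing.

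The size is unknown. A reader might also infer that the comparison of Dose 1 with Dose 2 is biased towards no difference. That would need the broad reading and a real difference in tolerability between doses, and it would affect only the per-period tables. The documents establish neither condition.

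The conclusion rests on version 1.0 of the main SAP. The booster SAP cites an addendum of October 2017 that is not among the documents reviewed.

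**What to change.** Change two sentences in the main SAP.

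1. In 3.3.3, replace the one-dose sentence with: *For subjects who do not receive the second vaccination, AEs from the first vaccination to the end of vaccination period 1, as set out in the General Definitions, are assigned to vaccination period 1.*
2. In 3.5.8, replace the additive sentence with: *The Overall summary counts all events in the overall vaccination period, that is, those in Period 1, those in Period 2 and any assigned only to the overall period.*

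The second change also covers events left unplaced by the worst-case principle. The booster SAP (4.3.3) already avoids that gap by sending unplaceable AEs to the active trial phase.

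The cost is two sentences and one programming condition, with no new data. If tables have already been produced, check the withdrawal row of Table 14.3.1.1 against Table 14.3.1.1.1 and Listing 16.2.7.1.6.

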### **Pre-treatment Adverse Events**

AEs recorded after signing of the informed consent form but before the first administration of trial vaccine are considered pre-treatment AEs. These pre-treatment AEs will be presented in a subject listing.

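### Adverse events with an incomplete start date are counted as treatment-emergent even when the recorded month, year or end date places them before the first vaccination

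*SAP*

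**What the plan says.** Three parts of the main-trial SAP (version 1.0, 31 May 2017) act on an adverse event whose start date is incomplete.

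- **Imputation (3.3.2, Partial/Missing Start Date).** With only the day missing, the first of the month is used, with one exception: "if the month is the same as the month of the first vaccination date then assign the imputed start date as the first vaccination date". With day and month missing, 1 January is used "unless the year is the same as the first vaccination date then assign imputed start date as the first vaccination date". With nothing recorded, the first vaccination date is used "unless the end date indicates that the AE/medication could have started/been taken prior to this". For that last exception the SAP prescribes 1 January and says which year to take: "in which case the date is imputed to 1st January of the same year as the start date".
- **Classification (3.3.3).** "If the start date is (partially) missing the AE will be regarded as a treatment-emergent AE following the worst-case principle".
- **Worst-case principle (3.3.3).** An imputed first-of-month or first-of-year date that matches the month and year of a vaccination goes to that vaccination period. The sentence after it begins "If the AE cannot be assigned to a vaccination period because of a (partially) missing start date then it will be only assigned to", and the destination it names is the overall vaccination period.

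Three definitions bear on the result. The SAP's General Definitions require a treatment-emergent event to start after a dose, on that day or in the following 28 days. SAP 3.5.8 says: "AEs recorded after signing of the informed consent form but before the first administration of trial vaccine are considered pre-treatment AEs", and sends these to a listing only. Protocol 8.1.2.1 likewise treats onset between consent and first vaccination as pre-treatment.

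**The concern.** A worst-case rule is sound where onset after vaccination is possible and the record cannot settle it. Here the rule also covers events for which the record does settle it. The same event then satisfies two definitions that should exclude each other, and a programmer cannot follow both. At stake is whether some screening-phase events enter the treatment-emergent tables, and whether a start can be imputed later than a known end. Since 3.3.2 consults the end date when the start is wholly missing, its authors accepted that an end date is informative; the two rules before it do not use it.

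**Working it through.** **Rules applied to test events.** The documents give no figure to reproduce, so the check applies the rules of 3.3.2 and 3.3.3 literally. The first vaccination is taken as 12 Oct 2016, an illustrative date that is not from the documents.

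| Case | Recorded start | Recorded end | Imputed start (3.3.2) | Status under 3.3.3 | Status on the recorded facts |
|---|---|---|---|---|---|
| 1 | Sep 2016, day missing | none | 1 Sep 2016 | treatment-emergent | pre-treatment |
| 2 | Oct 2016, day missing | 5 Oct 2016 | 12 Oct 2016, after the end | treatment-emergent | pre-treatment |
| 3 | 2016 only | 5 Oct 2016 | 12 Oct 2016, after the end | treatment-emergent | pre-treatment |
| 4 | wholly missing | 5 Oct 2016 | 1 January of an undefined year | treatment-emergent | pre-treatment |
| 5 | Oct 2016, day missing | none | 12 Oct 2016 | treatment-emergent | undetermined; a legitimate worst case |

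- Case 1: imputation keeps the known month, so the event has a pre-vaccination date and a treatment-emergent flag together. The override comes from the sentence in 3.3.3 alone.
- Cases 2 and 3: the first two imputation rules ignore the end date, and 3.3.3 then confirms the wrong status.
- Case 4: the rule takes the year from the start date, which is missing by definition; the end date must be meant. The table in 3.3.2 adds a second conflict, because it specifies no imputation of a start date when the year is missing.

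**How often the month alone decides.** Inputs: screening lasts up to 28 days (Protocol 4.2.1.1). Assumptions: Day 0 is uniform over a 365-day year, onset is uniform over a window of w days before Day 0, and only the day is missing.

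An onset o days before Day 0 falls in an earlier calendar month exactly when Day 0 is one of the first o days of its month. For o up to 28 this holds for 12 × o of the 365 dates, because every month has at least 28 days. Averaging over o = 1 to w:

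share = (12/365) × (w + 1)/2

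- w = 7: 12 × 4 / 365 = 48/365 = 13%
- w = 14: 12 × 7.5 / 365 = 90/365 = 25%
- w = 28: 12 × 14.5 / 365 = 174/365 = 48%

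Direct enumeration of 365 vaccination dates and 28 preceding days gives 47.7%, in agreement. In the remaining cases only the end date can show that onset preceded vaccination.

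**Booster SAP.** Section 4.3.3 repeats the unconditional sentence and sends unassignable events to the booster active phase. Section 4.3.2 repeats the two rules that ignore the end date and the reference to the year of a missing start date.

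**The case against.** The strongest defence is that the 3.3.3 sentence invokes the worst-case principle, which works from imputed dates and aims to avoid misclassification. On that reading an event imputed to an earlier month is simply pre-treatment; otherwise keeping the earlier month would serve no purpose for this classification. This is a sensible intention, but the text does not state it. Only the first sentence of the principle is tied to a matching month and year. The second sends any event left unassigned by a partial date to the overall vaccination period. The neighbouring words about events starting on or after vaccination do not help either, since for a partial date that is the question to be decided.

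A second defence is that SAP 3.5.8 classifies by when an event was recorded, so an event captured at screening, or at Visit 1 before dosing, can be recognised without a full date. In practice this could resolve some cases. The SAP, however, does not say that the recording visit takes precedence over 3.3.3, so the two sections still conflict.

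It is also fair that counting extra events is conservative for safety, and that listings show the original dates, so any case is visible. Both points stand and limit the importance of the issue.

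A reader might go further and infer that the end-date rule in 3.3.2 ("unless the month is the same as the month of the first vaccination date then impute the end date as the last vaccination date") distorts the tables as well. It often gives a date outside the recorded month, but events are assigned by onset, and durations are not calculated for partial dates (3.3.4). Medication tables ask only whether the end date is after the first vaccination (3.5.5). For a subject given both doses, the second-dose date and the month end answer that alike, unless Day 0 is the last day of its month. The practical effect is close to nil, so it is not part of this point.

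**Conclusion.** The point holds as a contradiction in the rules with a small effect. On the literal text, an event that provably began or ended before the first vaccination is counted as treatment-emergent, and an imputed start can fall after the recorded end. One imputation rule cannot be programmed as written.

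The effect is confined to events with onset between consent and first vaccination and an incomplete start date. The documents do not say how many there will be. The 13% to 48% range is a share of day-missing screening events only and depends on the uniformity assumptions. It is not a share of all treatment-emergent events; 48% applies only if events are spread over the full 28 days.

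Two stronger readings are not supported. The imputation rules do not discard an earlier known month: 3.3.2 keeps it, and 3.3.3 overrides it. Nor do the documents suggest a bias between arms, since these onsets precede randomisation at Visit 1; the likely result is a little noise. Treating undetermined dates, such as case 5, as treatment-emergent is correct and should stay.

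**What to change.** 1. **SAP 3.3.3, classification sentence.** Replace with: *An AE with a (partially) missing start date is treatment-emergent unless the known parts of the start date, or the end date, show that it began before the first vaccination; such an AE is pre-treatment.*
2. **SAP 3.3.2, start date, first two rules.** Assign the first vaccination date only if the end date is not before it; otherwise keep the default first of the month or 1 January.
3. **SAP 3.3.2, start date, third rule.** Take the year from the end date, and align the missing-year row of the table with this rule.
4. **SAP 3.3.3, worst-case principle.** Limit both sentences to events not shown to be pre-treatment under change 1. Without this, case 2 would be imputed to 1 Oct 2016, match the vaccination month, and be sent back into vaccination period 1.
5. **Booster SAP 4.3.2 and 4.3.3.** Make the matching changes relative to the booster vaccination.

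Under these rules cases 1 to 4 become pre-treatment and case 5 stays treatment-emergent. The cost is a few wording changes and the matching program edits, with no new data. If tables have already been produced, the affected events can be found from the listings.
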